8.2.1. Inclusion criteria

Patients must meet all the following inclusion criteria to be eligible for inclusion in the study:

1. Patient treatment with lorlatinib is initiated through Pfizer's expanded access program for treatment of ALK+ neuroblastoma.
2. HCP documentation of at least one tumor assessment of response after patient has had at least one dose of lorlatinib
3. Evidence of a personally signed and dated informed consent document indicating that the patient (or a legally acceptable representative, or a waiver of informed consent has been granted by the IRB/IEC) has been informed of all pertinent aspects of the study.

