8. METHODOLOGY FOR REAL WORLD DATA COLLECTION

The real world data (RWD) evaluation will involve supplemental collection of de-identified data collected on patients treated with lorlatinib for pediatric neuroblastoma who initiated treatment through Pfizer's expanded access program. Pediatric patients with ALK-aberrant neuroblastoma who are prescribed lorlatinib by their healthcare professionals (HCPs) and have met Pfizer expanded access program criteria will be eligible for inclusion in data collection. Supplementary data will be collected in partnership with Bionical Emas.

PFIZER CONFIDENTIAL

Prior to initiation of data collection activities, Bonical Emas, in collaboration with Pfizer, will develop a customized data collection tool (DCT) to capture data on demographics, clinical characteristics and outcomes. The length of the DCT will be kept to a minimum to avoid burden on participating institutions. The DCT will be made available to participating institutions through a web-based, electronic data capture (EDC) system.

During data collection, Bonical Emas will review the data on an ongoing basis, with HCPs contacted for clarification as required. Bonical Emas in conjunction with their statistical partner Syne Qua Non Limited (SQN) will summarize and report the data at timepoints detailed in [Section 5](#). Finally, a data collection report will be developed.

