8.1. Design of data collection

Up to 50 pediatric patients with ALK-aberrant neuroblastoma who initiated treatment with lorlatinib as part of expanded access program will be included.

The real world data collection will be initiated after the patient has been approved for expanded access to lorlatinib per Pfizer's expanded access program and the treating HCP has agreed to participate in data collection. All assessments described in this protocol are performed as part of normal clinical practice or standard practice guidelines for the patient population and healthcare provider specialty in the countries where this data collection is being conducted. Data from patients who have completed treatment, patients receiving ongoing treatment and new patients will be captured. A progress report will be developed for the patients who have completed treatment, with a more comprehensive final report descriptive in nature produced for the total population.

[figure not shown]

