8.2.2. Exclusion criteria

Patients meeting any of the following criteria will not be included in the study:

- 1, Any patient who does not meet any of the inclusion criteria defined in the previous section.

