8.5. Study size

With primary goal of the Pfizer expanded access program is to provide treatment access to patients with an unmet clinical need, no formal power calculations were conducted to determine sample size. Furthermore, the data collection does not involve hypotheses testing (via statistical testing) and it is primarily being conducted to understand treatment outcomes. Target sample size will comprise every patient fulfilling eligibility criteria above and providing informed consent for real world data collection.

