8.6. Data management

Bonical Emas will implement Data Management practices for collating and managing the data. These include (1) HCP access management and training, (2) data review, and (3) database storage and retention.

HCP Access Management and Training:

Bonical Emas will add HCPs to the EDC using details obtained from Pfizer after confirmation of patient eligibility and HCP agreement. HCP information will include: HCP name, country, location.

Data Review:

Data review is iterative process to ensure integrity and quality of data. Bonical Emas will ensure data are complete, reliable and processed correctly.

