8.6.1. Case report forms (CRFs)/Data collection tools (DCTs)/Electronic data record

As used in this protocol, the term DCT should be understood to refer to either a paper form or an electronic data record or both, depending on the data collection method used in this study.

A DCT is required and should be completed for each included patient. The completed original DCT are the sole property of Pfizer and should not be made available in any form to third parties, except for authorized representatives of Pfizer or appropriate regulatory authorities, without written permission from Pfizer. The HCP shall ensure that the DCTs

PFIZER CONFIDENTIAL

securely stored in encrypted electronic form and will be password protected to prevent access by unauthorized third parties.

The HCP has ultimate responsibility for the collection and reporting of all clinical, safety, and laboratory data entered on the DCT and any other data collection forms (source documents) and ensuring that they are accurate, authentic/original, attributable, complete, consistent, legible, timely (contemporaneous), enduring, and available when required. The DCT must be electronically signed by the HCP or by an authorized staff member to attest that the data contained on the DCT are true. Any corrections to entries made in the DCT or source documents must be dated, initialed, and explained (if necessary) and should not obscure the original entry.

In most cases the source documents are the hospital or the HCP's chart. In these cases, data collected on the DCT must match those charts.

In some cases, the DCT may also serve as the source document. In these cases, a document should be available at the HCP site and at Pfizer that clearly identifies those data that will be recorded on the DCT, and for which the DCT will stand as the source document.

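### Inclusion criterion 2 makes entry depend on a tumor assessment after the first dose, although outcomes are timed from treatment start; treated but unassessed patients may be left out of ORR, PFS and OS

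*Combined protocol and SAP*

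**What the plan says.** Section 8.2.1 opens with "Patients must meet all the following inclusion criteria to be eligible for inclusion in the study", and its second criterion is "HCP documentation of at least one tumor assessment of response after patient has had at least one dose of lorlatinib". Section 8.5 carries this into the sample: "Target sample size will comprise every patient fulfilling eligibility criteria above and providing informed consent for real world data collection". Section 8.6.1 ties the data record to inclusion: "A DCT is required and should be completed for each included patient".

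Other places describe the population differently:

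- Section 7 states its objectives for pediatric patients who started lorlatinib through the program, with no mention of assessment.
- Section 8 says that patients who are prescribed lorlatinib and "have met Pfizer expanded access program criteria will be eligible for inclusion in data collection".
- Section 8.7.2 produces summaries on all collected data, whether or not the inclusion and exclusion criteria are met.
- Section 8.7.5 computes ORR over a total population that is not defined. It times OS, PFS and duration of treatment from treatment start.

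Two further passages leave room for doubt. Section 8.2.2 excludes "Any patient who does not meet any of the inclusion criteria defined in the previous section", which read literally could remove only patients who meet none of the criteria. Section 8.6 adds HCPs to the EDC "using details obtained from Pfizer after confirmation of patient eligibility and HCP agreement", without saying whether that means program eligibility or eligibility for this study.

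**The concern.** A patient who dies, stops or is lost before any documented assessment fails criterion 2. If that patient is not entered, everyone in the data set has survived to a first assessment, yet the survival clock starts at the first dose. The time in between is then free of deaths by construction. Such a patient also cannot have a recorded CR or PR, so leaving the patient out shrinks the ORR denominator without touching the numerator.

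The risk is clearest for patients who completed treatment before January 2021 (Section 8.7.1), because their assessment status is already known when they are considered for entry.

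This is a series of up to 50 patients without a comparator, and Section 11 says its report will inform reporting to regulatory authorities. The denominator therefore matters. Section 8.9 describes selection through HCP willingness but does not mention selection on having an assessment.

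**Working it through.** The plan gives no power or sample-size figure to reproduce; 50 is a ceiling without a derivation. The check has a textual part and an arithmetical part.

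**Text.** Sections 8.2.1 and 8.5 together put an unassessed patient outside the sample. Section 8.7.2, and arguably Section 8, point the other way. Section 8.7.2 acts only on data already collected, and Section 8.6.1 requires a record only for included patients. Neither says whether an unassessed patient's data are entered.

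**ORR.** Let N be the number treated, m the number without an assessment and x the number of responders. Counting unassessed patients as non-responders, the all-treated ORR is x/N and the assessed-only ORR is x/(N−m). The ratio is N/(N−m), which exceeds 1 whenever m > 0 and x > 0. Example with assumed counts: 15/50 = 30.0% (Clopper-Pearson 95% CI 17.9 to 44.6%) becomes 15/47 = 31.9% (19.1 to 47.1%) with m = 3, and 15/44 = 34.1% (20.5 to 49.9%) with m = 6.

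**OS illustration.** Inputs:

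- Median OS 16.1 months and response rates of 20 to 64%, both from Section 6. These are background figures from other regimens, not planning values.
- Exponential survival (assumption).
- First assessment at t = 1 to 4 months (assumption). Section 8.2 anticipates visits every 3-4 months, linked to re-supply, but gives no assessment time.
- A share q of deaths before t is unassessed and omitted (assumption, 0.25 to 1).

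Formulas: λ = ln 2/16.1 = 0.04305; S(t) = exp(−λt); omitted fraction p = q(1 − S(t)). Among those entered, the median is −ln(0.5(1 − p))/λ, 12-month OS is S(12)/(1 − p), and ORR is the all-treated ORR divided by (1 − p). For all treated, the median is 16.1 months and S(12) = 59.7%.

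| t (months) | q | p | Omitted per 50 | Median OS (months) | 12-month OS | ORR 20% becomes | ORR 64% becomes |
|---|---|---|---|---|---|---|---|
| 1 | 0.25 | 0.0105 | 0.5 | 16.3 | 60.3% | 20.2% | 64.7% |
| 1 | 1 | 0.0421 | 2.1 | 17.1 | 62.3% | 20.9% | 66.8% |
| 3 | 0.25 | 0.0303 | 1.5 | 16.8 | 61.5% | 20.6% | 66.0% |
| 3 | 1 | 0.1212 | 6.1 | 19.1 | 67.9% | 22.8% | 72.8% |
| 4 | 0.25 | 0.0395 | 2.0 | 17.0 | 62.1% | 20.8% | 66.6% |
| 4 | 1 | 0.1582 | 7.9 | 20.1 | 70.9% | 23.8% | 76.0% |

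The ORR shift runs from about 0.2 points (20% to 20.2%) to 12.0 points (64% to 76.0%).

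**Direction of the OS bias.** Suppose 12% of treated patients are omitted, t = 3, and a share d of the omitted died before 3 months. Assume also that the omitted survivors have the same later survival as everyone else alive at 3 months. Then S_obs(u) = [S(u) − (1 − d) × 0.12 × S(u)/S(3)]/0.88 for u > 3. The median is 19.1, 17.4, 16.6 and 15.7 months for d = 1, 0.5, 0.25 and 0. Under that assumption the bias changes sign at d = 1 − S(3) = 12.1%; if the omitted survivors do worse later, it can be upward below that value. In the opposite case, omitting 5 of 50 patients who survive beyond 12 months moves 12-month OS from 59.7% to (0.5965 − 0.10)/0.90 = 55.2%.

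No size is given for PFS or duration of treatment, because the documents state no figure for either in this setting. A patient whose first assessment shows PD satisfies criterion 2 and stays in. The PFS bias therefore comes only from deaths or failures before any documented assessment.

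**The case against.** The strongest reply is that Section 8.2.1 is the operative list and the more general descriptions elsewhere are to be read subject to it. A reader might infer that Sections 8.1 and 8.2 contradict criterion 2. They do not. They are silent on assessment, as they are on patient consent, and "The real world data collection will be initiated after the patient has been approved for expanded access to lorlatinib" fixes a starting time rather than a sufficient condition for entry. That part of the reply stands: the real tension is between Section 8.2.1 and Section 8.7.2, with Section 8 arguably on the side of the latter. It does not remove the problem, because reading criterion 2 as decisive is exactly the case in which early deaths can be selected out.

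A reader might also infer that the omission would be invisible in the report. That holds only if these patients are never entered. If they are entered, Section 8.7.3 reports disposition, including death and loss to follow-up, and Section 8.7.8 commits to reporting the amount of missing data.

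It is also fair to say that the analyses are descriptive and untested (Section 8.7), that the sample is declared a convenience sample, and that with 15/50 responders the confidence-interval half-width is about 13 points, wider than any ORR shift in the table. These points lower the priority. They do not answer the concern, since the interval covers sampling error and not a systematic change of denominator.

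**Conclusion.** The concern holds as a should-fix point. Two things are firm. The text does not settle whether treated but unassessed patients are in the data or in the ORR population. If criterion 2 decides entry, ORR rises by the factor N/(N−m) relative to all treated.

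The upward bias in OS and PFS is conditional on the omitted patients being mainly early deaths or failures. It would be tempting to conclude that the reported OS and PFS will be too favorable, but the documents do not support that. They give neither the number unassessed nor the reasons, and omitted patients who live on, for example after loss to follow-up, offset the bias.

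The size is unknown, and is zero if all treated patients are entered. The illustrated ranges (median OS 16.3 to 20.1 months against 16.1; ORR shift about 0.2 to 12.0 points) rest on exponential survival, borrowed background rates and omission through early death alone. They are not bounds: omission for other reasons would raise m, and with it the ORR shift, further.

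**What to change.** 1. Delete criterion 2 as an entry condition. Align Sections 8, 8.2.1, 8.2.2, 8.5 and 8.7.2 to one population: all patients meeting criterion 1, with consent (from the patient or a legally acceptable representative) or an IRB/IEC waiver, who received at least one dose of lorlatinib, whether or not an assessment is documented.
2. In Section 8.7.5 define the total population for ORR as this set. Count patients who died, discontinued or were lost without an assessment as non-responders. At each milestone report their number and, separately, the number still on treatment and not yet assessed at the cut-off. The separate count is needed because Section 5 allows a last patient on 31 December 2023 and locks the database on 15 February 2024. That is 46 days, or about 1.5 months, against visits every 3-4 months.
3. Keep the assessed-only ORR as a labelled sensitivity analysis.

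The cost is wording, one or two extra rows in the best-overall-response table and a few more DCTs (about 0.5 to 8 per 50 in the illustration, which counts early deaths only). ORR, PFS and OS may come out slightly lower, and are unchanged if all treated patients would have been entered anyway. Delayed-entry or landmark analyses of OS and PFS could be added but are not needed to resolve the point.

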8.2.2. Exclusion criteria

Patients meeting any of the following criteria will not be included in the study:

- 1, Any patient who does not meet any of the inclusion criteria defined in the previous section.

8.3. Variables

Variables will include demographics at the start of lorlatinib treatment (age, gender, race, body surface area (BSA)), clinical characteristics (date of initial diagnosis, high risk at diagnosis, ALK aberration date of sample collection and testing, testing platform, ALK and other genetic mutations, ALK amplification, translocation or over-expression, and MYCN amplification, prior anti-cancer treatment, ALK inhibitor use, disease status), treatment start date, starting dose, resupply date(s), BSA, response assessment (date, disease status, HCP reported response, International Neuroblastoma Response Criteria (INRC) response assessment criteria²⁸ and assessment modality), last date of lorlatinib, patient alive, date of death, date of discontinuation of lorlatinib and reason for discontinuation of lorlatinib. Safety data will be collected in DCT as outlined in [Section 10](#).

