The identification of ALK as a critical factor in the development of neuroblastoma make it an attractive therapeutic target. Lorlatinib is a potent, brain-penetrant, third generation inhibitor of ALK.²¹ Lorlatinib overcomes almost all known ALK resistance mutations observed with other ALK TKIs.²² In preclinical models lorlatinib has exhibited superior potency towards ALK neuroblastoma tumor models.^{23,24} In addition, lorlatinib shows strong activity toward all tested ALK neuroblastoma mutations.^{23,24}

New Agents in Neuroblastoma Therapy (NANT) consortium has several ongoing clinical trials to identify best therapies and combination of therapies for treatment of pediatric patients with neuroblastoma. An on-going Phase 1 dose escalation clinical trial is assessing

PFIZER CONFIDENTIAL

the use of lorlatinib as a single agent in combination with chemotherapy in patients aged 1 to 90 years with relapsed/refractory neuroblastoma.²⁵ Recently presented results of this Phase 1 study showed inhibition of ALK driven neuroblastoma with lorlatinib occurred with manageable toxicity and objective anti-tumor activity was observed.²⁶

Pediatric high-risk neuroblastoma remains an area of high unmet need and poor outcomes in young children. Along with the promising early clinical data from the NANT study, we have noted several pediatric neuroblastoma patients being treated through Pfizer's expanded access program. This protocol details the real world data collection of data to evaluate the real world effectiveness of lorlatinib in pediatric neuroblastoma patients. Generating real world evidence from expanded access programs is becoming increasingly valuable, as this data has the potential to supplement regulatory submissions.²⁷

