7. RESEARCH QUESTIONS AND OBJECTIVES

The primary goal of the Pfizer expanded access program is to provide access to lorlatinib to patients with a serious or immediately life-threatening disease/condition who have exhausted all other standards of care and are not eligible for a clinical trial. Treatment is delivered by the healthcare professional (HCP) as sponsor of the expanded access request and according to a treatment plan approved institutional review board/independent ethics committee as required by local laws and regulations or institutional requirements.

The overall goal of this real-world data collection is to assess demographic, clinical characteristics and real-world effectiveness of pediatric neuroblastoma patients who initiated treatment with lorlatinib through an expanded access program. Data will be collected to address the following specific objectives:

1. Describe the demographic and clinical characteristics of pediatric neuroblastoma patients who initiated treatment with lorlatinib through an expanded access program
2. Evaluate the effectiveness of treatment with lorlatinib in pediatric neuroblastoma patients in terms of duration of treatment, HCP reported response, and duration of response
3. Estimate progression free survival and overall survival
4. Collection of safety data

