8.2. Setting

Clinical practice and treatment of each patient will follow as determined by each treating HCP individually. There will be no interference from Pfizer with the HCP's diagnostic and treatment decisions. The decision to treat a patient with lorlatinib will be prior to and independent of participation in the real world data collection and according to the clinical judgement of their HCP. Therefore, the data collection will in no way influence prescribing patterns or treatment decisions. If eligible, the patient will receive treatment through Pfizer's expanded access program independent of involvement in the collection of real world data.

HCPs treating a patient approved to receive lorlatinib via Pfizer's expanded access program will be invited to take part in the real world data collection. Upon HCP agreement, they will receive access to the EDC, where they can enter data into the DCT.

The first pediatric neuroblastoma patient received lorlatinib in March 2017 as part of expanded access programs and the program is ongoing. Data collection is anticipated to initiate in January 2021 and is estimated to have last patient entered into real world dataset at

PFIZER CONFIDENTIAL

the end in December 2023. Database lock would occur in February 2024, as outlined in [Section 5](#).

Data will be collected via DCT at multiple time points for patients who are receiving ongoing treatment. These timepoints will be determined by HCP standard practice for treatment and follow-up of their patients. Visits are anticipated to occur every 3-4 months, corresponding with re-supply of lorlatinib. Data will be collected on a continual basis until discontinuation of treatment with lorlatinib, death, loss to follow-up or end of study, whichever comes first.

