Partial Response (PR)	PR in at least one component and all other components are either CR, MD (Bone marrow), PR (Soft tissue or Bone) or Not involved (NI); no component with PD.													
Minor Response (MR)	PR or CR in at least one component but at least one other component with SD; no component with PD.													
Stable Disease (SD)	SD in one component with no better than SD or NI in any other component; no component with PD.													
Progressive Disease (PD)	Any component with PD													
Best Overall response	HCP Reported Response	Derived as the best overall response taking the HCP Reported Response observed up to the data cut-off date for a specific milestone. (The												

PFIZER CONFIDENTIAL

	Repeated using Derived Objective Response	sequence order from best to worst is CR, PR, MR, SD, PD.)
Overall Response Rate (ORR)	Best Overall Response	Derived as Best overall response of CR+PR of the total population observed up to the data cut-off date for a specific milestone.
Duration of response	Treatment Start and HCP Reported Response Date	Derived as (Date of PD or death, whichever occurs first) – (Date of PR or CR, whichever occurs first) + 1
Progression free survival (PFS)	Treatment Start and HCP Reported PD/Death Date	Derived as (Date of PD or death (by any cause in the absence of PD)) – (Treatment start date) + 1
Duration of treatment	Treatment Start and Stop Dates	Derived as (Treatment stop date) – (Treatment start date) + 1
Overall survival (OS)	Treatment Start and Death Dates	Derived as (Date of death) – (Treatment start date) + 1

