8.7.6 Statistical summaries

Demographic and clinical characteristics

The number and percentage of patients will be presented within each categorized variable. In addition, descriptive statistics for continuous variables will include the mean, standard deviation, median, interquartile range, minimum and maximum.

The demographics will also be presented by subgroups for any subgroups with more than 5 patients.

HCP's reported objective response

For each response component (with the exception of best response), the responses will be listed along with the date of the assessment. A derived objective response will be produced and compared to the HCP overall reported response for confirmation of robustness.

Best Overall Response (BOR) and Overall Response Rate (ORR)

For the BOR, the number and percentage of patients in each ordered category will be presented and summarized by baseline disease status. In addition, the ORR will be presented including the Clopper Pearson 95% Confidence interval.

PFIZER CONFIDENTIAL

Duration of response

The number and percentage of patients will be presented within each of the following categories for duration of response: 0 to <3 months; 3 months to <6 months; 6 months to <1 year; 1 to <2 years; 2 to <3 years >3 years; lost to follow-up. Kaplan-Meier (KM) estimates will be used to give the median, Q1 and Q3 duration of response, with 95% confidence limits. If a patient does not show symptoms of progressive disease, their duration of response will be censored at their last visit date prior to the data cut-off date.

Time to event

KM estimates will be presented, where possible, for duration of treatment, progression free survival and overall survival (i.e., time to death). The following censoring rules will be applied:

- Duration of treatment

Patients who have not discontinued treatment at the data cut-off date will be censored based on the last recorded date when the patient was known to be continuing treatment prior to the data cut-off date.

- Progression free survival

Patients who have not experienced PD or died at the data cut-off date will be censored at the date of last contact prior to the data cut-off date.

- Overall survival

[figure not shown]
Any patient not known to have died at the data cut-off date will be censored based on the last recorded date on which the patient was known to be alive prior to the data cut-off date.

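### Anti-cancer therapy given alongside lorlatinib is not specified for collection, so the plan cannot say whether its ORR, DOR and PFS describe lorlatinib alone or lorlatinib plus other active therapy.

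*Combined protocol and SAP*

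**What the plan says.** Section 7 sets objective 2 as follows: "Evaluate the effectiveness of treatment with lorlatinib in pediatric neuroblastoma patients". The measures are duration of treatment, HCP-reported response and duration of response. Objective 3 adds PFS and OS.

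Section 8.3 gives a field-level list of variables. Under clinical characteristics it has "prior anti-cancer treatment, ALK inhibitor use, disease status". It then gives lorlatinib dates, starting dose, resupply, response assessments, vital status and discontinuation. It lists no anti-cancer therapy given while the patient is on lorlatinib.

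Nothing restricts such therapy. Section 8.2 states: "Clinical practice and treatment of each patient will follow as determined by each treating HCP individually". The only exclusion in section 8.2.2 is "Any patient who does not meet any of the inclusion criteria defined in the previous section", and none of the inclusion criteria concerns concurrent treatment.

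Section 8.7.5 defines ORR thus: "Derived as Best overall response of CR+PR of the total population observed up to the data cut-off date". In section 8.7.6, DOR for patients without progression is handled by one rule: "their duration of response will be censored at their last visit date prior to the data cut-off date". PFS is censored at last contact. Neither rule mentions therapy added before progression. The treatment subgroup in section 8.7.7 is by prior therapy only, and section 8.9 does not list the point as a limitation.

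**The concern.** In a single-arm data collection, the label on the response rate carries the whole inference. If some children had chemotherapy, radiation or surgery while taking lorlatinib, their responses enter the ORR on the same footing as responses to lorlatinib alone. For example, a primary tumor resected during treatment could be recorded as a component complete response. A response or progression-free interval sustained by added therapy would likewise run on in DOR and PFS.

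Combination use is plausible. Section 6 says there is no standard approach after relapse, and it refers to a separate Phase 1 trial assessing "the use of lorlatinib as a single agent in combination with chemotherapy". That phrase is garbled, but it shows that lorlatinib with chemotherapy was a known option.

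What is at stake is attribution. Section 11 says the report will inform what is presented to regulatory authorities as needed, and section 6 notes that expanded access data may supplement submissions. A descriptive ORR must still say which treatment it describes. This is also more than a gap in wording: a sensible analyst cannot split results by a variable that nobody was asked to record.

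**Working it through.** The plan states no figure that bears on this point, and section 8.5 reports no power calculation. The check is therefore mainly textual, with one illustration.

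**Step 1. Is concurrent therapy captured anywhere?**

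- Section 8.3: prior anti-cancer treatment, plus ALK inhibitor use with no timing. Even if the second item covered concurrent use, it would not capture chemotherapy, immunotherapy, MIBG therapy, radiation, surgery or transplant.
- Section 8.7.7: these same therapy types appear, but only as categories of prior treatment.
- Section 10: concomitant medications are mentioned as information for follow-up of individual safety reports, described there as more detailed than what the DCT holds. Additional concomitant drug treatment is otherwise mentioned only as a criterion for calling a test finding an adverse event. Neither is an effectiveness variable.
- Section 8.9: silent.

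**Step 2. Could it occur, and would the endpoints absorb it?** Sections 8.2 and 8.2.2 permit it. BOR and ORR run to the data cut-off. DOR is censored only at last visit and PFS only at last contact. Nothing in sections 8.7.5 or 8.7.6 stops or flags an outcome reached after therapy is added during lorlatinib.

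**Step 3. Illustration of size (assumed inputs, not document figures).** Let p be the response rate on lorlatinib alone, q the rate with added therapy, and c the share of patients with added therapy. Then

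pooled ORR = (1 − c)·p + c·q, and the difference from p is c·(q − p).

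With p = 20% and q = 50%:

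| c | pooled ORR |
|---|---|
| 20% | 0.80 × 20 + 0.20 × 50 = 26% |
| 30% | 0.70 × 20 + 0.30 × 50 = 29% |
| 40% | 0.60 × 20 + 0.40 × 50 = 32% |

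A wider range takes c from 10% to 50% and q from 20% to 64%. That span for q is borrowed from the response rates that section 6 quotes across relapsed/refractory trials; those are not rates for lorlatinib with and without other therapy.

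- p = 20%: the difference runs from 0 (q = 20%) to 0.50 × (64 − 20) = +22 points, that is 42% reported against 20%.
- p = 30%: the difference runs from 0.50 × (20 − 30) = −5 points to 0.50 × (64 − 30) = +17 points.

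**Step 4. The same in counts.** Take 50 patients, the maximum in section 8.1, and the planned Clopper-Pearson 95% interval.

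- 20 responders of 50: 40% (26.4 to 54.8).
- If 5 of these responded with added therapy and are counted as non-responders: 15/50 = 30% (17.9 to 44.6).
- If 10 did: 10/50 = 20% (10.0 to 33.7).

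The interval expresses sampling error only; it makes no allowance for a mixture of treatments. The recounted rates are not estimates of the lorlatinib-alone rate. They show how far the answer depends on a variable that is not specified for collection.

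**The case against.** Several points on the other side have force.

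- **The list may not be exhaustive.** Section 8.3 is worded as what the variables will include, and section 8 says the DCT is still to be developed. A reader might infer that the data will certainly not exist. The documents support only that the data are not specified for collection.
- **Later therapy is largely outside observation.** A reader might extend the point to therapy started after lorlatinib. Section 8.2 ends collection at discontinuation, and section 9.3 makes that date the last visit, so responses and response durations on later therapy mostly go unobserved.
- **OS is different.** A reader might add OS to the affected endpoints. Survival that includes the effect of later treatment is a legitimate treatment-policy measure, and the text leaves unclear whether deaths after discontinuation are recorded. The point does not extend to OS.
- **Evidence for combination use is thin.** The Phase 1 trial is a different cohort. The statement in section 8.2, "There will be no interference from Pfizer with the HCP's diagnostic and treatment decisions", only marks the study as non-interventional. Section 7 describes patients who have exhausted standard options, which makes added therapy less likely but does not rule it out. No frequency is given.
- **Uninterpretable would be too strong.** The analyses are descriptive, and the stated goal is real-world effectiveness. Outcomes under usual care can be read as such, provided the plan says so. It does not.
- **Burden.** Section 8 deliberately keeps the DCT short. This bears on how much to add, not on whether the gap exists.

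What remains is the gap for therapy given during lorlatinib. None of these points fills it.

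**Conclusion.** The concern holds for therapy concurrent with lorlatinib and its effect on BOR, ORR, DOR and PFS. Followed as written, the plan could not tell outcomes on lorlatinib alone from outcomes on lorlatinib with other active therapy, while objective 2 presents them as the effectiveness of lorlatinib without a control arm. It should be corrected.

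The size is unknown. The 26-32% illustration rests wholly on assumed rates and shares, and the wider range of −5 to +22 points shows that even the sign is not settled. A reader might infer that the reported ORR will be inflated. The documents do not support that, because they give neither the frequency of added therapy nor response rates with and without it. The supported conclusion is that the planned data could not show whether, or how far, the ORR departs from the lorlatinib-alone rate.

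**What to change.** 1. **Section 8.3 and the DCT:** record type, start date and stop date of each anti-cancer therapy given while on lorlatinib, including surgery and radiation. The therapy categories in section 8.7.7 can be reused. State whether ALK inhibitor use means prior use, concurrent use or both.
2. **Section 8.7.6:** list these data. Present BOR and ORR for lorlatinib alone and for lorlatinib with concurrent therapy, and do the same for DOR and PFS where n is at least 5, the threshold in section 8.7.7.
3. **Optional:** a DOR and PFS sensitivity analysis censored at the start of added therapy, with a note that such censoring may be informative.
4. **Section 8.9:** state that outcomes otherwise reflect lorlatinib as used in practice, with or without other therapy.

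**Cost.** The DCT becomes slightly longer. The fields repeat for each therapy and need retrospective entry for patients treated since March 2017, but they come from the chart that the HCP already reviews. Subgroups will be small: with 50 patients and a share of 20-40%, the concurrent group would be 0.20 × 50 = 10 to 0.40 × 50 = 20, so the split is descriptive only. No patient's care changes.
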